- To describe the pharmacokinetic profiles of the nicotine and cotinine in a confinement setting in smokers switching from mCC to THS 2.2 Menthol as compared to smokers continuing to smoke mCC.
 - Peak (highest concentration along the day) on Day 5.
 - Time to peak (actual time when the peak was observed compared to the time of the first cigarette) on Day 5.
 - Weighted average concentration over 24 hours on Day 5.
- To describe the change in CYP1A2 enzymatic activity in smokers switching from mCC to THS 2.2 Menthol as compared to smokers continuing to smoke mCC, and to SA.
 - Molar metabolic ratio of paraxanthine/caffeine in plasma on Day 5 and Day 90 Visit.
- To monitor the safety profiles during the study.
 - Adverse events (AEs)/serious adverse events (SAEs), and device events including THS 2.2 Menthol malfunction/misuse.
 - Respiratory symptoms: cough assessment by visual analogue scale (VAS) and Likert scales and one open question.

- Vital signs.
- Spirometry.
- Electrocardiogram.
- Clinical chemistry, hematology, and urine analysis safety panel.
- Physical examination.
- Concomitant medications.
- To monitor selected risk markers in a confinement and ambulatory setting in smokers switching from mCC to THS 2.2 Menthol as compared to smokers continuing to smoke mCC and to SA.
 - Systolic and diastolic blood pressure on Day 6, Day 30 Visit, Day 60 Visit and Day 90 Visit.
 - High sensitive C-reactive protein (hs-CRP) , homocysteine, blood glucose, low density lipoprotein (LDL), high density lipoprotein (HDL), triglycerides (TG), total cholesterol (TC) in serum on Day 30 Visit, Day 60 visit, and Day 90 Visit.
 - Fibrinogen in plasma on Day 30 Visit, Day 60 visit, and Day 90 Visit
 - Hemoglobin A1c in blood on Day 90 Visit.
 - Soluble inter-cellular adhesion molecule-1 in serum on Day 6, on Day 30 Visit, Day 60 Visit and Day 90 Visit.
 - White blood cell (WBC) and platelet count in blood on Day 6, Day 30 Visit, Day 60 Visit, and Day 90 Visit.
 - 8-epi-prostaglandin F2 α (8-epi-PGF2 α) and 11-dehydro-thromboxane B2 (11-DTX-B2) in 24 hour urine on Day 5 Day 30 Visit, Day 60 Visit and Day 90 Visit (expressed as concentration adjusted to creatinine).
 - Body weight and waist circumference on Day 90 Visit.

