7.5.2.2 CYP1A2 activity test

CYP1A2 activity will be measured on Day 0, Day 5, and Day 90 Visit (Day 90). Measurement of enzyme activity will be based on the post-dose PX and CAF plasma molar concentrations approximately 6 hours (\pm 15 minutes) after the intake of one Tomerumin® (LionCorp.) caffeine tablet (around 170mg caffeine) with 150 ml \pm 10 ml water (Faber et al., 2004).

The exact time of intake of the caffeine tablet in the morning and of the time of blood sampling (the blood sample will be taken 6 hours [\pm 15 minutes] after the intake of the tablet) must be recorded. CYP1A2 activity will be assessed by measuring PX and CAF and calculating the PX/CAF molar metabolic ratio (Faber et al., 2004).

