Table 23 describes the expected power to demonstrate a reduction on all 5 primary BoExps in smokers switching from CC to THS 2.2 Menthol as compared to those continuing to smoke mCC, using one-sided test with 2.5% type I error probability using the assumptions from YVD-CS01-EU and ZRHX-EX-01 given a sample size of 160 smokers (~80 in THS 2.2, ~40 in CC, and ~40 in the SA arm). Therefore subjects will be enrolled into the study until there are 160 smokers in the FAS population.

Table 23. Expected power (YVD-CS01-EU and ZRHX-EX-01 studies assumptions)

Assumptions	Reduction					
	50%	51%	52%	53%	54%	55%
YVD-CS01-EU	94%	88%	81%	70%	56%	38%
ZRHX-EX-01	98%	97%	92%	76%	41%	6%

Power considerations related to secondary endpoints of biological changes:

The sample size is sufficient to obtain 95% confidence intervals for the ratio between (geometrical) mean levels of primary BoExps in THS 2.2 Menthol and SA with upper and

Data and information contained in this document are considered to constitute trade secrets and confidential commercial information, and the legal protections provided to such trade secrets and confidential information are hereby claimed under the provisions of applicable law. No part of this document may be publicly disclosed without the written consent of Philip Morris Products S.A.

lower limits deviating not more than 18% from the point estimates, with an 80% overall probability of achieving the desired precision of estimating the true mean.

This study has 80% power using a one-sided test with 2.5% type I error probability:

- To detect a 0.631 [mL/min/kg] (29%) difference between THS 2.2 Menthol and mCC in CYP1A2 activity, as measured by the caffeine clearance, assuming a standard deviation of 0.564. Effect size and variability are derived from data obtained in the (YVD-CS01-EU study sponsored by PMI.
- To detect a 24.71 [ng/g creatinine] (20%) difference between THS 2.2 Menthol and mCC in 11-DTX-B2, assuming a standard deviation of 43.78, as reported by Saareks et al., 2001. The anticipated effect size of THS 2.2 Menthol is assumed to be about 90% of the effect of smoking cessation reported in the paper by Saareks et al., 2001.

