As the calculation of the sample size was based on the primary objective (reduction of biomarkers levels in THS 2.2 Menthol relative to mCC), we assumed 50% of the subjects in the THS 2.2 Menthol arm would be using THS 2.2 Menthol exclusively and therefore will be included in the per-protocol population on Day 90.

In order to further optimize the assessment of BoExp and increase the comparability of the levels of BoExp between THS 2.2 Menthol and SA the confounding effects of the use of any other tobacco or nicotine containing product (other than the assigned product) need to be controlled for. Therefore a subject will be considered abstinent based on the following categorization:

- “Abstinence”: 100% abstinence from tobacco or nicotine containing product use other than the assigned product

- Predominantly abstinent not more than 0.5 uses of any tobacco or nicotine containing product (other than the assigned product) per day on average and no more than two uses on a single day occur.
- “Not abstinent”: more than 0.5 uses of any tobacco or nicotine containing product (other than the assigned product) per day on average or more than two uses on a single day occur.

The purpose of the defined threshold was to reduce the confounding effects of the use of any other tobacco or nicotine containing product (other than the assigned product). The results of a study PMI conducted in 2011 to evaluate the capacity of the urinary biomarker CEMA to detect smoking of small amounts of CC use (down to 2 CCs) per day was used to help us identify this threshold. The results of this study show that CEMA used as a urinary BoExp to acrylonitrile is able to discriminate between non-smokers and smokers who have smoked only 2 CCs and 4 CCs with a maximum level of sensitivity and specificity at an optimal threshold of the 2.56 µg/L (CEMA C_{max} in non-smokers) for CEMA and 3.76 µg/g for CEMA concentration adjusted to creatinine. For non-smokers CEMA and CEMA concentration adjusted to creatinine were greater than the LLOQ on only one occasion.

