12.6.2.4 CYP1A2 Activity

CYP1A2 activity will be measured in plasma on Day 0, Day 5 and Day 90. In this study the CYP1A2 activity will be calculated using the molar ratio of PX and CAF, as described in Section 7.1.3 "CYP1A2". Descriptive statistics of the values and percent change on Days 5 and 90 from Baseline and supportive listings will be provided.

The analysis will compare the log-transformed Day 5 values between the THS 2.2 Menthol and mCC arms and between the THS 2.2 Menthol and SA arms. ANCOVA models will be used on CYP1A2 activity levels with terms for log-transformed baseline, sex, average daily mCC consumption over the last 4 weeks as reported during screening and randomization arm. No adjustment will be made for multiple comparisons. If the results from the Day 5 analysis are significant (one-sided p-value ≤ 0.025) then the statistical significance will be repeated for the analysis at the Day 90 values. The SAS code will be similar to that described in Section 12.6.1.3 "Sensitivity Analysis".

Geometric LS means for each product along with the ratio (THS 2.2 Menthol :mCC) and 95% CI will be presented in the tables.

CYP1A2 activity will also be examined to compare the observed reductions in THS 2.2 Menthol vs. SA using the same methodology as above.

If there are any CYP1A2 assessments performed within 5 half-lives since the use of a concomitant medication affecting CYP1A2 activity, the analysis will be repeated by excluding these assessments for both the PP Set and FAS

All summaries and analyses will be performed on the FAS, and PP Set.

The data will be presented in the below outputs:

TFL number	Title
TABLES	
15.2.4.23.1	Descriptive Statistics of CYP1A2 Activity (%) – PP Set
15.2.4.23.2	Descriptive Statistics of CYP1A2 Activity (%) – FAS

TFL number	Title
15.2.4.24.1	Analysis of CYP1A2 Activity (%) – PP Set
15.2.4.24.2	Analysis of CYP1A2 Activity (%) – FAS
LISTINGS	
15.3.3.5	Listing of CYP1A2 Activity and Changes from Baseline

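### The 80% power stated for CYP1A2 is not what its printed inputs give (over 99.8%), and it describes caffeine clearance rather than the PX/CAF ratio that is analysed

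*Protocol*

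**What the plan says.** At the end of Protocol section 12.2, under the power considerations for secondary endpoints, one lead-in covers two bullets: "This study has 80% power using a one-sided test with 2.5% type I error probability".

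- CYP1A2: "To detect a 0.631 [mL/min/kg] (29%) difference between THS 2.2 Menthol and mCC in CYP1A2 activity, as measured by the caffeine clearance". The same bullet gives the spread in the words "assuming a standard deviation of 0.564", and both figures are attributed to an earlier confinement study by the sponsor.
- 11-DTX-B2: "To detect a 24.71 [ng/g creatinine] (20%) difference between THS 2.2 Menthol and mCC in 11-DTX-B2, assuming a standard deviation of 43.78".

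No arm sizes are printed with either bullet. Elsewhere section 12.2 plans about 80 THS 2.2 Menthol and 40 mCC subjects. It expects no exclusions from the per-protocol set in confinement, but expects half of the THS arm to be excluded in the ambulatory period, which leaves 40:40 (Table 22).

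The CYP1A2 endpoint in Protocol section 3.4.2 is "Molar metabolic ratio of paraxanthine/caffeine in plasma on Day 5 and Day 90 Visit". Protocol section 7.5.2.2 agrees: "CYP1A2 activity will be assessed by measuring PX and CAF and calculating the PX/CAF molar metabolic ratio". SAP section 7.1.3 defines the variable in the same way, and SAP section 12.6.2.4 sets the analysis: "The analysis will compare the log-transformed Day 5 values between the THS 2.2 Menthol and mCC arms", by ANCOVA with log baseline. Significance at Day 90 is considered only if Day 5 is significant. SAP section 8 repeats the primary power tables but not the secondary power statements.

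**The concern.** Two things look wrong. First, a difference larger than the standard deviation, with 40 or more subjects per arm, should give power close to 100%, not 80%. Second, neither document defines caffeine clearance in mL/min/kg as an endpoint or derived variable, so even a correct figure would not describe the planned test.

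What is at stake is how a CYP1A2 result is read, above all a non-significant one at Day 5, because Day 5 significance opens the Day 90 evaluation. Depending on how the statement is resolved, the difference detectable with 80% power at 80:40 could vary about twofold, and neither value is on the analysed scale. Section 12.2 is the only place in the two documents that gives this power.

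**Working it through.** **Inputs (Protocol section 12.2).** Difference δ = 0.631; SD = 0.564, taken to be in the same unit; one-sided α = 0.025; arms 80:40, or 40:40 for the Day 90 per-protocol set.

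**Method.** Two-sample t test without covariates. Noncentrality λ = δ / (SD × √(1/n₁ + 1/n₂)); power is the probability that a noncentral t with n₁ + n₂ − 2 degrees of freedom exceeds the critical value.

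**Control: the 11-DTX-B2 bullet.** The standardised difference is 24.71/43.78 = 0.564. At 80:40, √(1/80 + 1/40) = 0.1936, so λ = 0.5644/0.1936 = 2.91 and power is 82.4%. The method and the 80:40 arms therefore roughly reproduce the stated 80% for this item.

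**CYP1A2 as printed.** The standardised difference is 0.631/0.564 = 1.119.

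| Arms | √(1/n₁ + 1/n₂) | λ | Power (t) | Power (normal) |
|---|---|---|---|---|
| 80:40 | 0.1936 | 5.78 | 99.99% | 99.99% |
| 40:40 | 0.2236 | 5.00 | 99.86% | 99.88% |

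With these inputs, 20 THS and 10 mCC subjects would already give 79.6%.

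**Other readings tried (normal approximation).**

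| Reading | 80:40 | 40:40 |
|---|---|---|
| α halved to 0.0125 | 99.98% | 99.7% |
| SD multiplied by √2 | 98.3% | 94.3% |
| 29% reduction, 0.564 as log-scale SD | 88.0% | 77.5% |
| 29% reduction, 0.564 as CV | 92.0% | 83.0% |

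None comes within two points of 80%. The last two also contradict the printed mL/min/kg unit.

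**What would give 80%.** The standardised difference needed at 80:40 is 0.547. With SD 0.564 kept, the detectable difference is 0.547 × 0.564 = 0.309. If the printed 29% is relative to the mCC mean (an assumption), that mean is 0.631/0.29 = 2.18, and 0.309/2.18 is about 14%. With 0.631 kept instead, the SD would have to be 0.631/0.547 = 1.15.

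**The lead.** The CYP1A2 SD has the same three digits as the 11-DTX-B2 standardised difference. If 0.564 were δ/SD for CYP1A2 as well, the SD would be 0.631/0.564 = 1.119 and power at 80:40 would be 82.3%, next to the 82.4% of the control. The difference detectable with 80% power would then be 0.547 × 1.119 = 0.61.

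**Quantity.** The power statement is about caffeine clearance on its raw scale. The endpoint is the PX/CAF ratio on the log scale. No variance or expected ratio for PX/CAF is given, so its power cannot be computed from the documents.

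**The case against.** The strongest reply is that 80% is a floor. One lead-in serves both bullets, and at 80:40 both exceed it (82.4% and 99.99%). On that reading 0.631 and 0.564 may both be true values from the earlier study, and the only fault is loose wording. This cannot be excluded. It is a strained reading, because the sentence says the study has 80% power, not at least 80%, and 99.99% is far from 82%. But it means that a reader who infers a proven misprint goes beyond the documents.

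A reader might also take the digit match as proof that 0.564 is δ/SD. The text calls it a standard deviation, the source study is not available here, and the standardised difference for exactly 80% at 80:40 is 0.547, not 0.564. Under the same assumption about the 29%, an SD of 0.564 is a CV of 26% (0.564/2.18) and an SD of 1.119 a CV of 51%. Table 19 lists CVs from 0.20 to 0.70 for other markers, so it favours neither. The match is a lead and no more.

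Nor should a reader infer that the neighbouring statements fail. The 11-DTX-B2 figure roughly reproduces at 80:40, and the 18% precision statement reproduces for the four Day 5 markers with a THS/SA CV (at most 17.7%, for S-PMA). No change to either is asked for.

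Finally, the 40:40 case carries less weight here. CYP1A2 is compared on Day 5 first, when 80:40 is expected, and it is also analysed on the full analysis set.

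**Conclusion.** The point stands in a limited form. The stated 80% is not the power implied by the printed CYP1A2 inputs at either arm size, and the statement concerns a quantity that the trial does not analyse. The documents leave open whether 80% is a minimum or an input is wrong.

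The calculation assumes normal data with equal variances, no covariate adjustment, and an SD in the unit of the difference. Adjustment for baseline would, if anything, raise power and widen the gap from 80%. If the inputs are right, power for caffeine clearance is understated, not overstated.

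This is minor. CYP1A2 is a secondary endpoint under an objective worded as descriptive. The protocol ties the size of the trial to something else (section 12.3): "As the calculation of the sample size was based on the primary objective". A reader might infer that the trial is mis-sized; nothing here supports that.

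**What to change.** Check the CYP1A2 bullet in Protocol section 12.2 against the source calculation, then amend the wording:

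- If 0.631 and 0.564 are both right, state more than 99% power for 0.631, or 80% power for about 0.31 (14%) at 80:40. If 80% was meant as a minimum, say so.
- If an input is wrong, correct it. Whether 0.564 is δ/SD is the first thing to look at.
- In either case, recompute the figure for the log PX/CAF ratio, giving the expected ratio and variability used, or state that it applies to caffeine clearance and not to the analysed endpoint.

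The cost is one source check and a few words of text. No subjects are added and no analysis changes.

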12.3 Product use

The FDA Draft Guidance on Modified Risk Tobacco Product Applications Draft (Section VI-A-2) (FDA, 2012a), FDA requires that an MRTP Application should contain scientific evidence about the effect the product may have on tobacco use behavior among current tobacco users including consideration of areas such as the expected rates of use of the tobacco product by current tobacco users and the use of the tobacco product in conjunction with other tobacco products.

Although subjects being requested to use solely the product allocated to their respective study arm it is considered that during the ambulatory period not all subjects randomized to the THS2.2 Menthol arm might be exclusively using THS2.2 Menthol at all times during the study. Subjects may concomitantly use THS 2.2 Menthol and CC (dual-use). To assess dual use of THS 2.2 Menthol and CC, PMI has defined dual-use with regards to using THS 2.2 Menthol in the following way:

[figure not shown]
Dual-use will be calculated as percentage based on their reported THS 2.2 Menthol Tobacco Sticks consumption and the number of conventional cigarettes smoked (menthol and non-menthol) by study period:

- on Day 30, using the reported number of cigarettes and/or Menthol Tobacco Sticks consumption since time of Discharge,
- on Day 60, using the reported number of cigarettes and/or Menthol Tobacco Sticks consumption after Day 30 and
- on Day 90, using the reported number of cigarettes and/or Menthol Tobacco Sticks consumption after Day 60.

Data and information contained in this document are considered to constitute trade secrets and confidential commercial information, and the legal protections provided to such trade secrets and confidential information are hereby claimed under the provisions of applicable law. No part of this document may be publicly disclosed without the written consent of Philip Morris Products S.A.

Figure 2 presents a detailed overview on the definition of the product use categories:

Figure 2 - Product Use Pattern Categorization

The more granular categorization scheme will be used for the definition of the per-protocol population and for the description of the product use patterns observed in the study whereas the less granular scheme will be used for the presentation of other study endpoints (e.g. safety endpoints) to better understand the impact of product.

As the calculation of the sample size was based on the primary objective (reduction of biomarkers levels in THS 2.2 Menthol relative to mCC), we assumed 50% of the subjects in the THS 2.2 Menthol arm would be using THS 2.2 Menthol exclusively and therefore will be included in the per-protocol population on Day 90.

In order to further optimize the assessment of BoExp and increase the comparability of the levels of BoExp between THS 2.2 Menthol and SA the confounding effects of the use of any other tobacco or nicotine containing product (other than the assigned product) need to be controlled for. Therefore a subject will be considered abstinent based on the following categorization:

- “Abstinence”: 100% abstinence from tobacco or nicotine containing product use other than the assigned product

- Predominantly abstinent not more than 0.5 uses of any tobacco or nicotine containing product (other than the assigned product) per day on average and no more than two uses on a single day occur.
- “Not abstinent”: more than 0.5 uses of any tobacco or nicotine containing product (other than the assigned product) per day on average or more than two uses on a single day occur.

The purpose of the defined threshold was to reduce the confounding effects of the use of any other tobacco or nicotine containing product (other than the assigned product). The results of a study PMI conducted in 2011 to evaluate the capacity of the urinary biomarker CEMA to detect smoking of small amounts of CC use (down to 2 CCs) per day was used to help us identify this threshold. The results of this study show that CEMA used as a urinary BoExp to acrylonitrile is able to discriminate between non-smokers and smokers who have smoked only 2 CCs and 4 CCs with a maximum level of sensitivity and specificity at an optimal threshold of the 2.56 µg/L (CEMA C_{max} in non-smokers) for CEMA and 3.76 µg/g for CEMA concentration adjusted to creatinine. For non-smokers CEMA and CEMA concentration adjusted to creatinine were greater than the LLOQ on only one occasion.

12.4 Analysis Population

The per-protocol (PP) population will be the primary analysis for BoExp, and risk markers. The FAS will be the primary analysis set for compliance to randomization arm, exposure and questionnaires. Exposure and questionnaires will be described by randomization arm and according to the product use (exclusive THS 2.2 Menthol, dual-use of THS 2.2. Menthol and mCC, mCC exclusive, SA) groups.

A sensitivity analysis will be run on the compliant population for the for BoExp and risk markers.

The primary population for the assessment of safety will be the safety population. To evaluate the robustness of the interpretation of safety and the study level safety conclusions an additional subset of the safety analyses will also be presented on the full safety population, as specified in Section 12.6.5. Safety will be summarized and presented by randomization arm and according to product use (exclusive THS 2.2 Menthol, dual-use of THS 2.2. Menthol, Menthol and mCC, mCC exclusive, SA).

12.4.1 Full Analysis Set

The FAS consists of all the randomized subjects who had at least one post-randomization product use experience, if randomized to THS 2.2 Menthol or mCC, have at least one valid

non-safety assessment (THS 2.2 Menthol, mCC, SA arms). Subjects that were enrolled at the site that was terminated due to ICH/GCP uncompliance will be excluded from the FAS.

12.4.3 Safety Population

The safety population consists of all the subjects who had at least one exposure to THS 2.2 Menthol (product test at Admission Day). Subjects in the safety population will be analyzed according to actual exposure. Although subjects that were enrolled at the site that was terminated due to ICH/GCP uncompliance will be excluded from the safety population, they will be summarized within the Full Safety Population (see Section 12.4.4).

12.4.4 Full Safety Population

The full safety population consists of all the subjects who had at least one exposure to THS 2.2 Menthol (product test at Admission Day). Subjects in the full safety population will be analyzed according to actual exposure.

12.4.5 Compliant Population

The compliant population will be a subset of the PP Population for subjects from the THS 2.2 Menthol arm who are exclusive THS 2.2 Menthol users or exclusive mCC users, as defined in Section 12.3 or for subjects from the mCC arm.

